there are no computerized components of the model. In addition, the acquisition costs are affordable, with an initial investment of less than \$10,000 required to begin training.

Our preliminary data using the physical colonoscopy model and our SCOPE program have been encouraging. We have shown that SCOPE, based on the above four tasks, can be administered in less than 50 minutes per learner. We have identified the key metrics for incorporation into a scoring system and have accumulated validity evidence that the SCOPE scoring system objectively assesses the technical skills required to perform standard flexible endoscopy. For each of the four tasks, we have validity evidence that task scores reliably differentiate between novices, intermediates, and experts. Our data indicate that SCOPE is a reliable, simple program for simulating basic flexible endoscopy. SCOPE could be an ideal training platform to prepare for basic clinical endoscopy and FES testing.⁷⁻⁹

The goal of this proposal is to develop a proficiency based skills curriculum for FES using SCOPE. We will draw on the success of proficiency based training for FLS and apply the same methodologies to FES. A proficiency based skills curriculum for FES using SCOPE could help prepare learners for the FES examination and could foster the success of the entire FES program.

Hypothesis

Our hypothesis is that training to expert derived performance goals on a non-computer based flexible endoscopy simulator will allow a group of novice endoscopists to acquire a level of skill adequate to achieve a greater than 80% pass rate on the manual skills portion of the Fundamentals of Endoscopic Surgery (FES) assessment. After completing this proficiency based curriculum, these novice endoscopists will also demonstrate performance scores on the Global Assessment of Gastrointestinal Endoscopic Skills for Colonoscopy (GAGES- C) and Simulated Colonoscopy Objective Performance Evaluation (S.C.O.P.E.) assessments equivalent to intermediately experienced endoscopists (50 - 140 endoscopies). Finally, the group of novice endoscopists who complete this proficiency based curriculum will demonstrate significantly higher scores on FES, GAGES-C, and S.C.O.P.E when compared to a control group that simply undergoes repeat assessment without any formalized curriculum (to control for learning effect of repeated assessment).

Methods

Subjects: Two distinct categories of subjects will be needed:

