Data Analysis: For continuous variables, mean performance differences between pretest and posttest assessment within groups will be statistically assessed for significance using paired t-test. Mean performance differences between groups will be statistically assessed for significance with unpaired t-tests. Differences for multiple repeated measures during long term follow up will be assessed with repeated measure ANOVA. For proportions, rates of achieving a passing score on the FES assessment will be statistically assessed for significance using Fishers exact test or chi squared as appropriate.

Sample Size / Power Analysis

Samples size can be estimated using previous data for two of our primary endpoints stated in the hypothesis, GAGES-C and S.C.O.P.E. Previously published GAGES-C scores for novice and intermediate endoscopists⁶ showed a difference in means between the two groups of approximately 6, with a standard deviation in the novice group of 3.8 and intermediate group of 1.6. If we use a paired, two tailed t-test (since our subjects undergo a pre-test then a post-test) with alpha set at 0.05, estimated standard deviation of 5.5 and a power of 80%, then we need 9 subject to be able to reject the null hypothesis. Since the exact difference in performance improvement is unknown, Figure 1 shows sample size and power for a difference in means ranging from 3 to 6.

Similar calculations can be done using the S.C.O.P.E. score endpoint. Unpublished data currently undergoing peer review showed that for S.C.O.P.E score, novice and intermediate

endoscopists showed a difference in means between the two groups of approximately 115 with a standard deviation in the novice group of 94 and intermediate group of 62.⁹ If we apply the same paired, two tailed t-test with alpha set at 0.05, estimated standard deviation of 150 and a power of 80%, then we need 15 subject to be able to reject the null hypothesis. Since the exact difference in performance improvement is unknown, the graph below shows sample size and power for a difference in means ranging from 95 to 125.

[figure not shown]

Figure 2: Required sample size as a function of statistical power for differences in means between groups ranging from 95 - 125

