Based on these evidence based estimates, a sample size of 24 experimental subjects would allow us to be well powered across a broad range of differences in mean performance. If we allow for a 20% drop out rate, since participation is completely voluntary, that would result in recruiting 30 novice experimental subjects. or 10 subjects / site. In a separate analysis conducted similar to the ones above (not shown), approximately 12 control subjects would be required to reject the null hypothesis between the experimental and control groups with an 80% power. Applying the 20% drop out rate to the control group brings the target subject recruitment to 15, or 5 / site.

Comparison of the ES group with other groups is not part of our hypothesis testing, as this group serves to establish the reference criteria for the GAGES assessment and the proficiency scores for S.C.O.P.E. An estimated recruitment of up to 10 subjects per site should be more than adequate to ensure a broad representation of the desired skill set.

SAGES RESEARCH GRANT APPLICATION BUDGET SHEET

09BudgetSheet

Detailed budget for 12 month period from __ Jul. 1, 2013 through Jun. 30, 2014.

Dollar amount requested (Omit cents) _____ 30,000

Total for the grant request may not exceed \$30,000.

* Salary funds should be used for staff required to execute the study, but should not be used for salary support for the primary investigator. If salary support exceeds 50% of the project budget, then specific justification is required.

**Funds requests for travel for the presentation of a SAGES funded study should be limited to \$1,000.

NAME	POSITION TITLE	TIME/EFFORT		SALARY	FRINGE BENEFITS	SUB-TOTALS
		%	Hrs/ Week			
1. [name]	Principal Investigator*	5	2			
2. [name]	Assoc. Investigator	4	1.5			0
3. [name]	Assoc. Investigator	4	1.5			0
CONSULTANT COSTS						
EQUIPMENT						
(List all Items&Total Equipment Cost)		Items				Subtotal
SUPPLIES						
(List all Items&Total Supplies Cost)		Items Kyoto Colonoscopy SCOPE Models (6 at \$2,500 each, total \$15,000), Colon Inserts (6 at \$1,000 each, total \$6,000), MacBook pro computer 13 inch (3 at \$1,300 each, total \$3,900), Mac Software \$660, Misc recording / simulator maintenance supplies \$190				25,750
TRAVEL**						
(List all Items & Total Cost)		PI site visit travel to Tulane and UMD two visits each \$3,250, SAGES meeting travel for presentation - \$1000				4,250
PATIENT CARE COSTS						
CONSORTIUM/CONTRACTUAL COSTS						

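### The 80% between-group power claimed for 12 controls names no endpoint or SD; at the section's own planning values it is about 85% for GAGES-C but 56% for S.C.O.P.E.

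*Protocol*

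**What the plan says.** The Hypothesis section expects trained novices to score higher than untrained controls on FES, GAGES-C and S.C.O.P.E. It gives the reason for the control arm as "to control for learning effect of repeated assessment". Under Methods, Phase II, novices are randomised 2:1, and the Data Analysis paragraph compares groups with unpaired t-tests.

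The Sample Size / Power Analysis section counts GAGES-C and S.C.O.P.E. among the primary endpoints and sizes both on a paired pre-post test.

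- **GAGES-C:** the difference is about 6. The published groups are quoted with a "standard deviation in the novice group of 3.8 and intermediate group of 1.6". The SD entered is 5.5 and the result is 9 subjects. A range of 3 to 6 is plotted.
- **S.C.O.P.E.:** the source groups differ by about 115, with SDs of 94 for novices and 62 for intermediates. The calculation then takes an "estimated standard deviation of 150 and a power of 80%, then we need 15 subject to be able to reject the null hypothesis". A range of 95 to 125 is plotted.

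The section settles on 24 evaluable trained subjects. The control arm follows in one sentence, which reports a separate calculation of the same kind that is not shown. Its result is that "approximately 12 control subjects would be required to reject the null hypothesis between the experimental and control groups with an 80% power". Allowing for 20% dropout, the recruitment targets are 30 and 15.

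**The concern.** The randomised comparison is the only one that separates the effect of training from the effect of taking the tests twice. Its power rests on one unqualified figure with no endpoint, difference or SD attached. The calculation is described as similar to those shown, so a reader will try the planning values that are on the page. They support the figure for one primary endpoint and not for the other.

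The two planning SDs are also hard to reconcile with the group SDs quoted beside them, so a reader cannot tell which spread the between-group claim assumes.

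If S.C.O.P.E. power is really near 56%, a non-significant S.C.O.P.E. result could be read as evidence that the curriculum does not work, when the trial had little better than an even chance of detecting the planned effect.

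**Working it through.** All power figures are exact (noncentral t), two-sided 5%.

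**1. The paired figures.** The noncentrality is (difference / SD) × √n, with n − 1 degrees of freedom.
- GAGES-C, 6 / 5.5: n = 8 gives 75.4% and n = 9 gives 81.7%. The stated 9 is reproduced.
- S.C.O.P.E., 115 / 150: n = 15 gives 78.8% and n = 16 gives 81.7%. The stated 15 is one short, which is not pressed here.

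**2. The 12 controls.** With 2:1 allocation, the number of controls needed for 80% is:
- GAGES-C, 6 / 5.5: 11 (22 v 11 gives 81.6%; 20 v 10 gives 77.6%). This is close to the stated 12.
- S.C.O.P.E., 115 / 150: 21 (42 v 21 gives 80.6%).
- S.C.O.P.E., 115 with the novice SD of 94: 9. At 1:1 allocation it is exactly 12 per group (81.7%), but the design is 2:1.

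**3. Power at 24 v 12.** The noncentrality is (difference / SD) / √(1/24 + 1/12) = 2.828 × difference / SD, with 34 degrees of freedom and critical value 2.032.

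| Endpoint | Difference | SD | Noncentrality | Power |
|---|---|---|---|---|
| GAGES-C | 6 | 5.5 | 3.09 | 85% |
| GAGES-C | 5 | 5.5 | 2.57 | 70% |
| GAGES-C | 4 | 5.5 | 2.06 | 52% |
| GAGES-C | 3 | 5.5 | 1.54 | 32% |
| S.C.O.P.E. | 125 | 150 | 2.36 | 63% |
| S.C.O.P.E. | 115 | 150 | 2.17 | 56% |
| S.C.O.P.E. | 105 | 150 | 1.98 | 49% |
| S.C.O.P.E. | 95 | 150 | 1.79 | 41% |

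With all 30 and 15 recruits retained, S.C.O.P.E. at 115 / 150 gives 66%.

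**4. What 80% would require.** At 24 v 12 the standardised difference must be 1.02. That is 1.02 × 150 ≈ 153 S.C.O.P.E. points or 1.02 × 5.5 ≈ 5.6 GAGES-C points. For a S.C.O.P.E. difference of 115, the SD may be at most 112 in whole points.

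**5. S.C.O.P.E. at 115 with the quoted group SDs, 24 v 12.**
- 94 in both arms: 92%.
- 62 in trained and 94 in controls (Welch): 95%.
- Pooled, √((94² + 62²)/2) = 79.6: 98%.

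**6. The planning SDs.** The SD of a difference satisfies SD² = s₁² + s₂² − 2·r·s₁·s₂, and is largest at r = −1, where it equals s₁ + s₂.
- GAGES-C: the maximum is 3.8 + 1.6 = 5.4, below the 5.5 used. Solving for r gives (14.44 + 2.56 − 30.25) / 12.16 = −1.09, which is impossible.
- S.C.O.P.E.: the maximum is 94 + 62 = 156, so 150 is possible. Solving for r gives (8836 + 3844 − 22500) / 11656 = −0.84. For comparison, r = 0 gives an SD of 112.6 and r = 0.5 gives 82.8.

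**7. Illustration only: retest gain in controls.** The protocol gives no figure. If controls gained an assumed 20% of the planned improvement, the net differences would be 92 and 4.8. Power at SDs 150 and 5.5 would be 39% for S.C.O.P.E. and 67% for GAGES-C. With the 62 / 94 SDs, S.C.O.P.E. would keep 82%.

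**The case against.** The strongest reply is that no arithmetic error has been shown. The 12 controls carry no endpoint, and GAGES-C at 6 / 5.5 yields 11, close enough to be the source. The SD of 150 is given for a paired test and is never stated as an input to the unpaired one. If posttest scores are compared, the group SDs are the natural choice and S.C.O.P.E. power exceeds 90%. An SD that looks too large is conservative for the paired calculation, and if 150 is too large then 56% understates the power.

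Much of this stands, and it rules out three stronger readings that a reader might infer.

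- **That the true power is 56%.** This is conditional on SD 150. The protocol does not say whether posttest or change scores are compared between groups, so neither 56% nor a figure above 90% can be called the power of the trial.
- **That 150 contradicts 94 and 62.** It does not; it only needs an implausible correlation. The protocol also never says that 5.5 and 150 were derived from the group SDs. If the posttest spread equalled the novice SD, the implied correlations would be −0.05 for GAGES-C and −0.27 for S.C.O.P.E., both possible.
- **That the paired and between-group calculations used different SDs.** An SD of 112.6 gives 80.1% at 24 v 12, while the paired n would then be 10, not 15. That is suggestive, but the between-group calculation is not shown, and the SDs of a change and of a score may properly differ.

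The reply does not rescue the sentence as written. It makes one unqualified claim in a section with two named primary endpoints. The GAGES-C explanation leaves S.C.O.P.E. uncovered and holds only near the top of the 3 to 6 range. The explanation by group SDs uses a spread other than the one the section chose for planning. Nor is this detail that can be left to an analysis plan, because the protocol itself states the power.

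**Conclusion.** The concern holds in a limited form. The single 80% is not supported for both primary endpoints by the section's planning values. At 24 v 12 those values give 85% for GAGES-C at a difference of 6, falling to 32% at 3. They give 56% for S.C.O.P.E. at 115, and nowhere above 63% in the plotted range. These figures assume equal SDs of 5.5 and 150 in both arms and no retest gain in controls. With the quoted S.C.O.P.E. group SDs the answer becomes 92% to 98%, so the conclusion turns on an SD that the section neither names for this comparison nor justifies. Separately, 5.5 cannot be obtained from 3.8 and 1.6, and 150 from 94 and 62 is possible but implausible. The trial is not shown to be underpowered; its stated power cannot be relied on for S.C.O.P.E. until the inputs are given.

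**What to change.** In Sample Size / Power Analysis, replace the one-line 80% claim with the power of the randomised comparison at 24 v 12, separately for GAGES-C and S.C.O.P.E. For each, state whether posttest or change is analysed, the SD of that quantity and its source, and the assumed difference net of any retest gain in controls.

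- If 5.5 and 150 are kept, say why, and report 85% and 56%, or detectable differences at 80% power of about 5.6 GAGES-C and 153 S.C.O.P.E. points.
- If a smaller SD is justified, use it in both the paired and the between-group calculations wherever the analysed quantity is the same, and update the paired n.

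The cost is rewording one section and possibly a less favourable S.C.O.P.E. figure. No added subjects and no change of test are asked for.

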Novice subjects (NS): 45 novice subjects will be recruited. (See power analysis) Inclusion criteria include any healthcare professional adult >18 years of age who has not had significant previous experience with a flexible endoscopic simulator and has performed less than 10 endoscopies (EGD and colonoscopy). Significant endoscopic simulator experienced is defined by self reported time on any endoscopic simulator of greater than 5 hours, or having previously completed a formalized endoscopy training curriculum. Professional backgrounds include but are not limited to medical students and resident physicians. Subjects will be recruited regardless of pregnancy status. Subject data will be identified in databases only by subject number. No identifying data will be recorded and performance will in no way affect any subjects course grading or evaluation on any rotation.

Experienced subjects (ES): 30 experienced subjects will be recruited (see power analysis) Inclusion criteria include any gastrointestinal healthcare professional adult >18 years of age who has performed more than 50 endoscopies. Professional backgrounds include and are limited to General Surgery PGY ≥4, Gastroenterology fellows, General, Colorectal, and Minimally Invasive Surgeons, and Gastroenterologists. Subjects will be recruited regardless of pregnancy status. Subject data will be identified in databases only by subject number. No identifying data will be recorded and performance will in no way affect any subjects grading or evaluation on any rotation, or credentialing.

Apparatus and Procedures:

Kyoto Colonoscopy Simulator: A non-computer based physical colonoscopy model manufactured by Kyoto Kagaku Co Ltd, Japan. A plastic external form contains a latex simulated colon that can be configured into different "cases" based on the standard inserts included. This model must be used in conjunction with a colonoscope with capabilities for insufflation, irrigation, and suction, connected to an imaging system and displayed on a 4:3 aspect ratio video monitor.

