Phase I: *Establishing performance goals and references*- This phase will involve the ES group to define the task specific training goals for the novice curriculum. Each ES subject will complete a GAGES-C assessment followed by 3 trials of each of the S.C.O.P.E tasks. Three trials are used to help ensure that the simulator specific learning curve has been accounted for. The GAGES-C scores will be used to help calibrate performance of experienced endoscopist on the Kyoto model as the GAGES-C data to date has come from actual colonoscopies. The mean trial 3 performance on each of the S.C.O.P.E. tasks will be used to set the proficiency levels for the training curriculum to be utilized in Phase II.

Phase II: *Assessing the effects of the curriculum*- The NS group will be randomized in a 2:1 ratio between the training group (NST) and the control group (NSC) respectively. Both groups will undergo a pretest consisting of a GAGES-C assessment, a S.C.O.P.E assessment, and an FES assessment. Subjects in the NST group will then train to the proficiency levels established in Phase I for each of the S.C.O.P.E. tasks. The NST group will then undergo a posttest

[figure not shown]
consisting of a GAGES-C assessment, S.C.O.P.E assessment, and FES assessment within 2 weeks of completion of the curriculum. NSC subjects will receive no training during this phase and will return for the posttest after the same amount of time as it took for the NST group to complete their training. Both groups will be queried as to any additional clinical endoscopic experience that they received between the pretest and the posttest. Once the NSC subjects complete the posttest, they will be allowed to complete the curriculum if they wish, including an additional post curriculum assessment within 2 weeks of curriculum completion.

Phase III: Long term follow up- All subjects who complete the curriculum in both the NST and NSC groups will be asked to return for additional assessment at 6 months and 12 months. Subjects will be queried as to any additional clinical endoscopic experience that they received between the assessments. This follow up assessment will consist of 3 trials of each S.C.O.P.E. task to evaluate for rapid spontaneous recovery of skills seen in previous similar studies.³ They will also undergo an FES assessment.

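### The hypothesis that trained novices match intermediate endoscopists has no planned analysis that could support it: the only enrolled comparator is excluded from testing, and only tests for a difference are listed.

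*Protocol*

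**What the plan says.** - **Hypothesis.** After the curriculum, novices are expected to reach GAGES-C and S.C.O.P.E. scores on "assessments equivalent to intermediately experienced endoscopists (50 - 140 endoscopies"; the range closes at 140.
- **Sample Size / Power Analysis.** It refers to "two of our primary endpoints stated in the hypothesis, GAGES-C and S.C.O.P.E", so these scores are not exploratory. It then says of the experienced group: "Comparison of the ES group with other groups is not part of our hypothesis testing". The reason given is that the group supplies the GAGES reference criteria and the S.C.O.P.E. proficiency scores.
- **Subjects.** "30 experienced subjects will be recruited", and eligibility is anyone in the listed gastrointestinal professions "who has performed more than 50 endoscopies". There is no upper limit, no intermediate stratum and no quota for one.
- **Data Analysis.** Within-group changes are tested by paired t-test and long-term follow-up by repeated-measures ANOVA. For the rest: "Mean performance differences between groups will be statistically assessed for significance with unpaired t-tests". FES pass rates are tested by Fisher's exact or chi-squared test.
- **Phase I.** "Each ES subject will complete a GAGES-C assessment followed by 3 trials of each of the S.C.O.P.E tasks". The same section says that GAGES-C data so far come from real colonoscopies, not from the Kyoto model.
- **Appended abstract on S.C.O.P.E. as a non-computer assessment tool.** An earlier cohort of 13 intermediates (51-139 colonoscopies) had a mean total S.C.O.P.E. score of 334 (95% CI 296-372). The protocol does not name it as the benchmark for this hypothesis.

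**The concern.** A claim of equivalence needs a comparator, a margin and an analysis that can reject a meaningful shortfall. A missing margin alone could be left to a statistical analysis plan. Here, though, the protocol itself states the hypothesis in one section and withdraws the only enrolled comparator in another, and a later plan cannot follow both.

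At stake is a headline claim on two primary endpoints: that simulator training brings novices to intermediate level. The planned analyses can show that novices improved, and that they beat untrained controls. Neither result says where they stand relative to intermediates.

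**Working it through.** **1. The plan's own figures.** Paired two-sided t-test, alpha 0.05, 80% power, by the noncentral t distribution:
- GAGES-C: difference 6, SD 5.5. n = 9 gives power 0.817; the plan's 9 reproduces.
- S.C.O.P.E.: difference 115, SD 150. n = 15 gives 0.788 and n = 16 gives 0.817; the plan's 15 reproduces to within one subject.
- Dropout: 24/0.8 = 30 and 12/0.8 = 15; both reproduce.

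The sizing is therefore sound for what it addresses, which is a pre/post gain and a trained-versus-control difference. None of it addresses equivalence to intermediates.

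**2. A significant gain does not show intermediate level.** The smallest significant mean gain with n = 24 is t(0.975, 23) × SD/√24:
- GAGES-C: 2.069 × 5.5/√24 = 2.3, against a gap of 6.
- S.C.O.P.E.: 2.069 × 150/√24 = 63, against a gap of 115.

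A trained group could pass this test with just over a third (2.3/6 = 0.38) or just over half (63/115 = 0.55) of the gap closed.

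**3. A non-significant difference from intermediates would not show equivalence.** The plan does not schedule this comparison; the check asks whether the listed t-test could serve if it were added.
- From the protocol: 24 trained novices, intermediate S.C.O.P.E. SD 62, novice SD 94.
- Assumed: trained-novice SD between 62 and 94, and 10 to 30 intermediates, because the protocol gives no count.
- Formula: SE = √(62²/n + s²/24), with Welch degrees of freedom and the noncentral t.

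For a true 40-point deficit (40/115 = 35% of the gap), the two-sided 5% test is non-significant with probability:

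| Intermediates | SE (s = 62 / 94) | P(non-significant) |
|---|---|---|
| 10 | 23.3 / 27.4 | 0.63 / 0.71 |
| 15 | 20.4 / 25.0 | 0.53 / 0.66 |
| 30 | 17.0 / 22.3 | 0.36 / 0.58 |

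**4. What a proper test could deliver.** The protocol gives no margin. For illustration, take half the novice-intermediate gap: 115/2 = 57.5, rounded to 58. One-sided 2.5% non-inferiority power for S.C.O.P.E. when the true means are equal:

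| Intermediates | Power (s = 94 to 62) |
|---|---|
| 5 | 0.33-0.36 |
| 10 | 0.53-0.65 |
| 15 | 0.62-0.79 |
| 30 | 0.72-0.92 |

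For GAGES-C with margin 3 (half of 6), intermediate SD 1.6, trained-novice SD 1.6 to 3.8 and 15 intermediates, power is 0.91 to 1.00.

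Two one-sided tests (TOST), closer to the word equivalent, are more demanding. For S.C.O.P.E. at 57.5 points, one-sided 5% and novice SD 94, power is 0.31 to 0.63 with 10 to 30 intermediates.

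**5. Could the historical cohort serve?** For S.C.O.P.E. it is plausible. The tasks are the same, 51-139 nearly matches the hypothesis's range, and the abstract's means (334 − 218 = 116) agree with the 115 used for sizing. But its interval half-width is (372 − 296)/2 = 38, a third of the gap. For GAGES-C, published values come from live colonoscopy, so they are not a like-for-like standard for a Kyoto-model score.

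**The case against.** The strongest reply is that the sentence excluding ES comparisons gives its reason: ES is a calibration group. On that reading the equivalence hypothesis is a loosely worded descriptive benchmark, and the randomised comparison carries the inference. This is a fair account of what may have been intended, and it is why rewording is an acceptable remedy. It does not remove the conflict, because the text states the claim as a hypothesis and calls the scores primary endpoints. Nor is the whole-group ES mean a benchmark for 50 to 140 endoscopies while experts are included in it.

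Three stronger readings are tempting, and the documents do not support them.
- A reader might infer that the question cannot be answered at all. A historical intermediate S.C.O.P.E. value is in the document, and the ES group may well contain suitable subjects. The gap is in the plan and can be repaired.
- A reader might infer that the investigators will take a non-significant t-test as proof of equivalence. Nothing says so. Step 3 of the working shows only that the listed test would not be adequate.
- A reader might infer that an adequately powered comparison is available with no extra recruitment. With no quota or upper limit, the number of intermediates is unknown, and S.C.O.P.E. power is poor if it is small.

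The half-gap margin is also open to challenge: 334 − 58 = 276 lies below the historical intermediate interval. It illustrates scale and is not a recommended value.

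**Conclusion.** Wrong as written. The Hypothesis and the power section conflict, and following the plan exactly would leave the equivalence hypothesis without an analysis that could support it. This conclusion rests on the text alone. The probabilities and power figures depend on assumed numbers of intermediates, the protocol's group SDs, and an illustrative margin.

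A secondary limitation concerns order. ES subjects take GAGES-C before their three S.C.O.P.E. trials, which the protocol includes to allow for the simulator's learning curve. Trained novices take theirs after extensive practice on the same platform. This plausibly favours the novices, but the size is unknown. It should be stated as a limitation; the documents do not establish that the session order is an error.

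The FES pass-rate hypothesis and the trained-versus-control hypothesis are untouched.

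**What to change.** Reconcile the Hypothesis with the power section in one of two ways.

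**(a) Keep the claim and make it testable.**
- Record each ES subject's endoscopy count and name those with 50 to 140 as the comparator. Cite the historical cohort (334, 95% CI 296-372, n = 13) as a supporting S.C.O.P.E. benchmark.
- Amend the sentence that excludes ES comparisons accordingly.
- Judge the claim by the confidence interval for trained novices minus intermediates against a pre-stated, justified margin, by non-inferiority or TOST. If non-inferiority is chosen, change the word equivalent to match.
- State that precision depends on the number of intermediates, with a range such as that in step 4 of the working.

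**(b) Make it descriptive.** Reword the hypothesis as a benchmark, report trained-novice and intermediate means with confidence intervals, and make no equivalence claim.

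Under either option, note the GAGES-C order as a limitation.

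**Cost.** Option (b) is wording only. Option (a) needs one recorded variable, a defended margin and possibly a recruitment quota for intermediates. Even then the S.C.O.P.E. claim may be underpowered and have to be reported descriptively. The choice should be made before ES testing begins, while experience can still be recorded prospectively and a quota set.
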